9.12. Other Examinations

Not applicable.

10. OTHER ASSESSMENTS

10.1. COVID-19 Assessments

All confirmed or suspected COVID-19 infection events during the study must be recorded in the eCRF. Investigator should make every effort to collect or perform all required diagnostic tests to fully diagnose the suspected concomitant illnesses to confirm the definitive diagnosis if possible. The subject's consent may be required for some of the diagnostic tests as required by the local legal or regulatory needs or customary practices.

In the case of a moderate to severe COVID-19 infection or COVID-19 infection requiring treatment, study drug interruption should be considered by the Investigator in consultation with the medical monitor.

In an effort to ensure appropriate safety reporting of COVID-19 cases in accordance with Health Authority guidelines, the following process should be followed for cases that have occurred in the context of a clinical trial:

- All confirmed or suspected COVID-19 events must be recorded in the eCRF.
 - Subjects who test positive for COVID-19 should be reported as "Confirmed COVID-19," either as an AE or SAE.
 - Subjects whose medical history and clinical manifestations, signs, and possible exposure are consistent with COVID-19 but for whom no polymerase chain reaction or antibody test for COVID-19 is available should be reported as "Suspected COVID-19," either as an AE or SAE.
- The usual protocol mandated SAE reporting requirements should be followed for confirmed or suspected COVID-19 as done for any other AE, ie, the Investigator should assess whether any seriousness criteria are met per protocol, and appropriate protocol reporting requirements should be followed.
 - In the event that the Investigator assesses that a COVID-19 case does not meet any seriousness criteria as outlined in the protocol, it should be reported as a nonserious adverse event in the CRF.
- All study drug interruption or discontinuation due to the COVID-19 event must be recorded on the AE and drug administration eCRFs.
- For both serious or nonserious COVID-19-related AEs, the following information should be provided as applicable:
 - Date and laboratory results confirming the COVID-19 diagnosis (including viral antigen test and/or antiviral antibody serological test).
 - Clinical course of the case including presenting signs, symptoms, exposure, actions taken with the investigational products, medications used for treatment or prophylaxis of COVID-19, and outcome in relevant eCRF (eg, concomitant medication, AE).
 - Findings from diagnostic imaging (including computed tomography scan or other chest imaging).

11. STATISTICAL METHODS

11.1. General Statistical Considerations

Continuous variables will be summarized by the number of subjects, mean, standard deviation, median, and minimum and maximum values, unless otherwise specified. Categorical variables will be summarized by using frequency counts and percentages. In general, data will be summarized by treatment group.

Raw data will be presented with the exact precision with which they were collected.

There is no multiplicity adjustment.

11.2. Analysis Sets

- All Enrolled Subjects will include all subjects who sign the informed consent form.
- The Intent-to-treat Analysis Set will consist of all randomized subjects.
- Safety Analysis Set will include all subjects who received at least 1 dose of study drug.
- Per-protocol Analysis Set consists of all randomized subjects who received at least 1 dose of the study drug according to an automatic voice or web response system assignment and do not have important protocol deviations. Important protocol deviations are defined in the statistical analysis plan (SAP).
- Pharmacokinetic Analysis Set will include all subjects who receive at least 1 dose of study drug and have at least 1 measurable pharmacokinetic result.
- Biomarker Analysis Set will consist of all subjects who receive at least 1 dose of study drug and have at least 1 measurable biomarker assessment.

11.3. Study Population Data

Disposition and reasons for ending the treatment and discontinuing from the study will be summarized and listed for subjects in the enrolled analysis set.

Demographic and other baseline characteristics will be summarized for the Intent-to-treat Analysis Set.

11.4. Efficacy Analyses

Not applicable.

11.5. Pharmacokinetic/Pharmacodynamic/Biomarker Analyses

11.5.1. Pharmacokinetic Analyses

Pharmacokinetic analyses will be based on Pharmacokinetic Analyses Set.

The following PK parameters will be calculated by noncompartmental methods from the DS-1211a concentration-time data: maximum plasma concentration, minimum plasma

concentration, time to reach maximum plasma concentration, and if appropriate area under the plasma concentration-time curve (AUC), terminal elimination half-life, The apparent total body clearance, and apparent volume of distribution at steady state. The PK analysis will be conducted in compliance with DSI Noncompartmental Analysis Guidelines.

Plasma concentration of DS-1211a and PK parameters will be summarized by treatment group using descriptive statistics, including the mean, geometric mean, standard deviation, coefficient of variation percentage or median.

Finally, plasma concentration data for DS-1211a collected from the study may also be analyzed by means of nonlinear mixed-effect modeling. Results from the analysis will be reported in a separate standalone report.

11.5.2. Pharmacodynamic Analyses

[figure not shown]
See Section 11.5.3.

11.5.3. Biomarker Analyses

All biomarker analyses will be based on Biomarker Analysis Set. Observed values at each assessment and the absolute change and percentage change from baseline will be numerically summarized for primary and exploratory biomarkers by treatment group over time. The 95% confidence interval will be presented for percentage change from baseline in ALP, PPi, and PLP. The baseline of biomarker data is defined as the last nonmissing assessment collected prior to the first dose of study medication.

Difference in primary and exploratory biomarkers between active doses and placebo will be summarized by descriptive statistics.

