I understand that the Sponsor may decide to suspend or prematurely terminate the study at any time for whatever reason; such a decision will be communicated to me in writing. Conversely, should I decide to withdraw from execution of the study, I will communicate my intention immediately in writing to the Sponsor.

Print Name	Signature
Title	Date (DD MMM YYYY)

SUMMARY OF CHANGES

Please refer to the comparison document for Protocol Version 3.0 (dated 16 Jan 2023) versus Protocol Version 2.0 (dated 03 Oct 2022) for actual changes in text. The Summary of Changes below is a top-line summary of major changes in the current DS1211-A-U201 clinical study protocol (Version 3.0) by section.

[figure not shown]
Amendment Rationale:

CONVENTIONS USED IN THIS SUMMARY OF CHANGES

All locations (section numbers and/or paragraph/bullet numbers) refer to the current protocol version, which incorporates the items specified in this Summary of Changes document.

Minor edits, such as update to language that does not alter original meaning, update to version numbering, formatting, change in font color, corrections to typographical errors, use of abbreviations, moving verbiage within a section or table, change in style, or change in case, are not noted in the table below.

CONVENTIONS USED IN THIS SUMMARY OF CHANGES				
CCI				

PROTOCOL SYNOPSIS

Protocol Title

A Phase 2, 12-Week, Randomized, Double-Blind, Placebo-Controlled Study of DS-1211b in Individuals with Pseudoxanthoma Elasticum

Protocol Number

DS1211-A-U201

Sponsor/Collaborators

Daiichi Sankyo, Inc.

Registry Identification(s)

TBD: NCT Number: ###, EudraCT Number: 2022-000676-19, or RCT Number: ### as applicable]

IND Number

IND Number 135092

Study Phase

Phase 2

Study Design

Study DS1211-A-U201 is a 12-week, randomized, double-blind, placebo-controlled, parallel-group study that aims to assess the safety, tolerability, and pharmacokinetic (PK) and pharmacodynamic (PD) dose response of DS 1211b in individuals with pseudoxanthoma elasticum (PXE) by using biomarkers relating to tissue-nonspecific alkaline phosphatase (TNAP) inhibition.

of DS 1211b or placebo in tablet form for once daily dosing for a total of 12-week dosing, followed by a postdose biomarker assessment and a 2-week follow-up safety check. Approximately 12 to 16 individuals with PXE will be enrolled in each group.

Study Completion

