2.1. Study Objectives

The objectives, definitions of associated endpoints as well as applicable outcome measures are described in Table 2.1. Further requirements for the endpoint analyses and censoring rules, where applicable, can be found in Section 11.4 Section 11.5, and Section 11.6.

Study results, based on the analysis of below endpoints, will be analyzed to assess the dose for future clinical trials.

Table 2.1: Description of Objectives, Outcome Measures, and Endpoints

Objectives	Outcome Measure	Endpoints	Category				
Primary							
To assess the safety and tolerability of DS-1211b compared with placebo in subjects with PXE	Title: Safety parameters during the study Description: Descriptive statistics of safety endpoints Time frame: From the time the subject signs the study ICF and up to Day 98 (14 days after the last dose of study drugs)	Incidence of AEs, including SAEs, and treatment-emergent AEs, physical examination/assessment findings including vital sign measurements, standard clinical laboratory parameters, and ECGs	Safety				
To assess the dose response by assessing the treatment changes in PD endpoints	Title: PD endpoints Description: Profiles of ALP and TNAP substrates Time frame: Data are collected at baseline through Day 98.	ALP, PPi, and PLP	Pharmacodynamic				
Secondary							
To characterize the PK of DS-1211a (the free form of DS-1211b in plasma) in subjects with PXE Title: PK endpoints Description: Plasma concentration and PK parameters of DS-1211a Time frame: Data are collected at baseline through Day 84.		Plasma concentration and PK parameters of DS-1211a Include, but are not limited to, Cmax, Tmax, Ctrough, AUCtau, AUClast, and AUCinf (if possible to calculate)	Pharmacokinetic				

[figure not shown]

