Coagulation	Х	X	X	Х	х		X	PT, aPTT and INR; predose (V2 to V5). Blood collection should follow ECG and vital signs if indicated at the same timepoint.
Chemistry	Х	X	X	Х	Х	Xe	X	Fasting required at all visits ^e except the postdose visit (Visit 6). Blood collection should follow ECG and vital signs if indicated at same timepoint. See Section 9.8 for details
Urine analysis	X	X			X			Fasted, use spot urine

Period	Screening	Baseline	Tre	atment	Period	Postdose	Follow-up	Notes
Visit Number	1	2	3	4	5 (EOT)	6	7	
Study Day	- 30 to -1	1	15	43	84ª	Last dose+3 ^{b,c}	98°	^a Or day of early discontinuation. ^b To be scheduled at 2 to 4 days after last dose (eg, Visit 5 or early discontinuation). ^c In-home visit unless otherwise specified by Investigator.
Window (days)			±3	±3	±3	±1	±5	
Pregnancy test	х	X	х	Х	Х		Х	Serum pregnancy tests to be performed at V1 Screening Visit. Urine pregnancy test to be performed at V2, V3, V4, V5, and V7. If positive, a serum pregnancy test should be performed.
Pharmacokinetic Assessments								
PK Sampling		X ^f	Xg	Xg	X^{f}			fFull collection/ § Sparse collection (See Table 3.2) Central laboratory testing. Blood collection should follow ECG and vital signs if indicated at same timepoint. Sampling will be obtained under nonfasted condition except for the predose samples, which will be collected after an overnight fast (≥ 8 hours). The windows for blood sample collection are as follows: 120 minutes at the predose timepoint and by ±10% of the nominal sampling time thereafter.
Pharmacodynamic Assessments								
ALP, PPi, and PLP	Xh	X ^f	Xg	Xg	X ^f	$\mathbf{X}^{\mathtt{h,i}}$	$X^{\mathrm{h,i}}$	fFull collection/g Sparse collection (See Table 3.2) h Single timepoint sample collection i ALP and PLP only Central laboratory testing. Blood collection should follow ECG and vital signs if indicated at same timepoint. All samples will be obtained under nonfasted condition except for the predose samples (Visits 2 to 5), which will be collected after an overnight fast (≥8 hours). The windows for blood sample collection are as follows: 120 minutes at the predose timepoint and by ±10% of the nominal sampling time thereafter.

Period	Screening	Baseline	Treatment Period			Postdose	Follow-up	Notes
Visit Number	1	2	3	4	5 (EOT)	6	7	

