5.1.2. Method of Treatment Allocation

Eligible subjects will be randomized in a 1:1:1:1 ratio into the 4 treatment groups (DS-1211b or placebo). The randomization schedule will be generated by an independent biostatistician. Prior to treatment, a randomization number will be assigned to each eligible subject. The randomization assignment will be implemented by an automatic voice or web response system.

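### The baseline of ALP, PPi and PLP is used only to form change and percentage change; a baseline-adjusted active-versus-placebo estimate would remove the effect of chance imbalance at almost no cost

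*Combined protocol and SAP*

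**What the plan says.** Table 2.1 (Section 2.1) lists among the primary objectives: "To assess the dose response by assessing the treatment changes in PD endpoints". The endpoints are ALP, PPi and PLP, and the same section says the results will help assess the dose for later trials. Section 3.2 calls the balance between PPi and PLP increases critical to that choice.

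Section 11.5.2 only refers to Section 11.5.3, which contains four relevant statements:

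- Baseline: "The baseline of biomarker data is defined as the last nonmissing assessment collected prior to the first dose of study medication".
- Summary by treatment group over time: "Observed values at each assessment and the absolute change and percentage change from baseline will be numerically summarized".
- Interval: "The 95% confidence interval will be presented for percentage change from baseline in ALP, PPi, and PLP".
- Between arms: "Difference in primary and exploratory biomarkers between active doses and placebo will be summarized by descriptive statistics".

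The synopsis gives the size: "Approximately 12 to 16 individuals with PXE will be enrolled in each group". Section 5.1.2 describes 1:1:1:1 allocation to four groups and states no stratification factor. Section 11.9 says the sample size has no statistical basis. Section 11.10 leaves further methods to an SAP, and no separate SAP text was supplied.

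**The concern.** Subtracting or dividing by baseline is not the same as adjusting for it. If the correlation rho between baseline and follow-up is below 1, an arm that happens to start low tends to rise by regression to the mean, and an arm that starts high tends to fall. A difference in mean change then mixes part of the baseline imbalance with the drug effect. In arms of 12 to 16, sizeable imbalances are common, and nothing in the visible design or analysis guards against them.

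At stake is how cleanly three active doses can be read against placebo, and against each other, on markers meant to inform dose selection. Adding an interval to the planned difference, or averaging a different statistic, would not cure this.

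**Working it through.** **Inputs.** From the documents: four arms and n = 12 to 16 per arm. Assumed: rho from 0.3 to 0.9, and log-scale SD equal to 1 at both baseline and follow-up. The documents give no rho, SD, effect size, alpha or power, so the plan has no figure of its own to reproduce.

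**Step 1: chance imbalance.** The baseline difference between two arms has SD √(2/n): 0.41 (n=12) or 0.35 (n=16). The probability that it exceeds 0.5 SD is 2[1 − Φ(0.5/√(2/n))].

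- n=12: 0.5/0.41 = 1.22, giving 22%.
- n=16: 0.5/0.354 = 1.41, giving 16%.
- At least one of three doses against the shared placebo arm (simulation): 47% (n=12) or 35% (n=16).

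**Step 2: conditional bias.** Given a baseline difference D (active minus placebo), the difference in mean change is shifted on average by −(1 − rho)D. At rho 0.5 and D = 0.5 SD the shift is 0.25 SD. The standard error of the change difference at rho 0.5 is √(2(1 − rho) × 2/n), which is 0.41 (n=12) or 0.35 (n=16). The shift is therefore about 0.6 to 0.7 of a standard error. Averaged over randomizations D is zero, and so is the bias.

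**Step 3: precision.** Per-subject variance is 2(1 − rho) for change and 1 − rho² after adjustment, a ratio of (1 + rho)/2. Estimating the common slope multiplies the adjusted variance by 1 + 1/(4n − 6): 1.024 (n=12) or 1.017 (n=16). Intervals use t with 4n − 4 df (change) and 4n − 5 df (adjusted).

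| rho | Variance, change | Variance, adjusted | Ratio | Interval narrower by (n=12 / n=16) | Shift from a 0.5 SD imbalance in change |
|---|---|---|---|---|---|
| 0.3 | 1.40 | 0.91 | 0.65 | 18% / 19% | 0.35 SD |
| 0.5 | 1.00 | 0.75 | 0.75 | 12% / 13% | 0.25 SD |
| 0.7 | 0.60 | 0.51 | 0.85 | 7% / 7% | 0.15 SD |
| 0.8 | 0.40 | 0.36 | 0.90 | 4% / 4% | 0.10 SD |
| 0.9 | 0.20 | 0.19 | 0.95 | 1% / 2% | 0.05 SD |

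At rho 0.5 the half-width falls from 0.82 to 0.72 SD (n=12) or from 0.71 to 0.62 SD (n=16).

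**Step 4: simulation check.** In 20,000 four-arm trials at rho 0.5, adjustment cut the variance by 23.3% (n=12) and 24.5% (n=16). The formula with slope cost gives 23.2% and 23.7%. The change difference correlated about −0.50 with baseline imbalance; the adjusted difference correlated about 0. For percentage change in lognormal data (CV 20% to 50%, no drug effect) the correlation was −0.47 to −0.49, so it behaves like log change.

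**Step 5: unequal SDs.** With baseline SD s0 and follow-up SD s1, the variance saved is (s0 − rho·s1)², out of s0² + s1² − 2·rho·s0·s1 for change. Take s0 = 0.7 and s1 = 1. At rho 0.5 the saving is 0.04/0.79 = 5%. At rho 0.7 it is zero, and the slope cost is then a small net loss.

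**The case against.** The strongest objection is that this is a small descriptive study and that the SAP may already hold an adjusted model. The second part cannot be excluded: Section 11.10 defers methods to the SAP, and Section 11.5.2 contains a figure that is not shown. Nothing supplied shows that the comparison is adjusted, however. Section 3.2 also announces modeling and simulation for the recommended dose, which is a second route to dose selection. It describes no baseline-adjusted comparison, but it means imbalance need not pass straight into the dose chosen.

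Several stronger readings are tempting and are not supported:

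- *The plan commits to unadjusted change for its between-arm comparison.* Section 11.5.3 names no scale for that difference. If observed values are compared, adjustment saves rho² of the variance instead: 25% at rho 0.5 and 49% at 0.7.
- *The planned analysis is biased.* The bias is conditional on the imbalance that occurs; over randomizations it averages to zero.
- *Power is being lost.* No hypothesis test is planned, and Section 11.9 rests on no power calculation.
- *Percentage change makes it worse.* Step 4 does not show this; it would need an assumed multiplicative drug effect.
- *Randomization is known to be unstratified.* Section 5.1.2 is silent, which is weaker.

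The reliance on rho and on equal SDs also stands as an objection. Section 4.2 excludes ALP below the lower limit of normal and PLP above the upper limit, which truncates entry values, so equal SDs cannot be presumed.

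**Conclusion.** The point holds as a cheap improvement to a primary comparison, not as an error that invalidates it. In the supplied text the baseline enters only through change and percentage change, and chance imbalances above 0.5 SD are likely enough at this sample size to matter. Adjustment makes the estimate free of that imbalance and, with equal log-scale SDs, narrows the interval by between 18–19% (rho 0.3) and 1–2% (rho 0.9). If the markers are very stable within subjects, or if baseline SD is close to rho times follow-up SD, little is gained over change. Section 11.9 cites Phase 1 intra- and intersubject variability, so the sponsor may be able to place rho within this range.

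**What to change.** In Section 11.5.3 and the SAP, add for ALP, PPi and PLP a baseline-adjusted estimate with 95% interval of each active-versus-placebo difference. Take it at the scheduled predose samples of Visits 3, 4 and 5, with Visit 5 as the key timepoint. Use an ANCOVA of log value on treatment and log baseline across all four arms, and back-transform to a ratio to placebo. A repeated-measures version is optional. Keep the planned observed, change and percentage-change profiles as they are.

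The cost is a few lines of text and one standard model per marker and visit on data already collected: no new samples, visits or subjects. Statistically it costs one covariate (about 2% of variance) and a common-slope assumption on the log scale. If the SAP already contains such a model, aligning Section 11.5.3 with it is enough. Section 11.10 has the SAP finalized before database lock, so the model should be written in by then.

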6.3. Treatment Period

Approximate visit durations are expected to be:

- Visits 1, 6, and 7: a few hours
- Visit 3 and 4: more than 6 hours
- Visits 2 and 5: more than 10 hours

Visits 1 through 5 are fasting visits (overnight fast [≥8 hours]). Study participants will be allowed to eat after the first blood collection.

Visits 6 and 7 will be conducted as in-home visits unless requested by the study participant or Investigator.

Study participants should withhold the intake of vitamin B6 or vitamin B6-containing supplements on the day of the study visits (Visits 1 to 7). Vitamin B6 or vitamin B6-containing supplements can be resumed after all study-related procedures are completed.

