8.2. Pharmacodynamic Assessment(s)

Venous blood samples will be collected for the measurement of ALP, PPi, and PLP following the sampling schedule in Table 3.1 and Table 3.2.

The windows for PD blood sample collection and details on assessment times and deviations are as follows: 120 minutes at the predose timepoint, and by \pm 10% of the nominal sampling time thereafter. Changes of biomarker levels from baseline will be calculated on the basis of plasma concentration-time data.

Biomarker samples will be analyzed by using a qualified analytical method for each marker.

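### The only planned 95% CI for ALP, PPi and PLP is on within-arm change from a normally fasted baseline, so at nonfasted times it cannot separate drug from meal or time of day

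*Combined protocol and SAP*

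**What the plan says.** **Baseline.** Section 11.5.3: "The baseline of biomarker data is defined as the last nonmissing assessment collected prior to the first dose of study medication". This is normally the Visit 2 (Day 1) predose sample. If that is missing, the rule falls back to the single screening sample.

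**Fasting state of the PD samples.** The ALP/PPi/PLP row of Table 3.1 (Section 3.3) says "All samples will be obtained under nonfasted condition except for the predose samples (Visits 2 to 5"), the predose samples being taken after an overnight fast of at least 8 hours. Section 6.3 adds: "Study participants will be allowed to eat after the first blood collection". Visits 2 and 5 have full PD collection, and Visits 3 and 4 have sparse collection. Visits 6 and 7 each have one sample, footnoted "h Single timepoint sample collection i ALP and PLP only".

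**Analysis.** Section 8.2: "Changes of biomarker levels from baseline will be calculated on the basis of plasma concentration-time data". Under Section 11.5.3, observed values and absolute and percentage changes are "numerically summarized for primary and exploratory biomarkers by treatment group over time", with a 95% CI on percentage change for ALP, PPi and PLP. The CI is not limited to particular times. The difference between active doses and placebo gets descriptive statistics, and no interval is stated for it.

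**Two fasting rules conflict.**
- Visit 7 is nonfasted in the PD row, and Section 6.3 does not list it as a fasting visit. The chemistry row of Table 3.1 says "Fasting required at all visits ^e except the postdose visit (Visit 6"), which makes Visit 7 a fasting visit.
- Visit 1 is fasting in Section 6.3 ("Visits 1 through 5 are fasting visits (overnight fast [≥8 hours"]), but the PD row counts its sample as nonfasted.

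**The concern.** A post-dose sample differs from the Day 1 predose sample in three ways: drug exposure, fed or fasted state, and clock time. Table 3.1 has no pre-treatment PD profile day that would supply a reference at matching times. A within-arm percentage change at a post-dose time therefore estimates the drug effect plus whatever meal and time-of-day shift the marker has. The planned interval is centred on that sum.

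The contrast that would remove a shift common to all arms, active against placebo at the same nominal time, is planned without an interval. Precision is thus reported for the quantity that mixes the effects and not for the one that separates them.

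ALP, PPi and PLP are the primary PD endpoints, and Section 2.1 says the results will be used to assess the dose for future trials. Section 3.2 treats the balance between the rise in PPi and the rise in PLP as critical to that choice. If a meal moved the two markers differently, the within-arm summaries at fed times would misstate the balance.

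**Working it through.** **No figure to reproduce.** The protocol gives no SD, effect size or meal effect for these markers, and Section 11.9 states that the sample size has no statistical basis. The check therefore compares states from the text and then gives an illustration whose shift is an assumption.

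**Step 1: fasting state against the usual baseline (Day 1 predose, fasted).**

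| PD sample | Markers | State in PD row | Same state as baseline? |
|---|---|---|---|
| Visits 3, 4, 5 predose | ALP, PPi, PLP | Fasted | Yes |
| Visits 2 to 5 post-dose | ALP, PPi, PLP | Nonfasted | No |
| Visit 6 | ALP, PLP | Nonfasted | No |
| Visit 7 | ALP, PLP | Nonfasted (chemistry row: fasting) | Unclear |

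Visits 6 and 7 follow the last dose, so they show offset of effect and not effect on treatment.

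**Step 2: within-arm interval under an assumed shift.** Inputs: n = 12 to 16 per arm (synopsis); four arms, 1:1:1:1 (Section 5.1.2). Let b be a shift common to all arms, in units of the SD of percentage change (assumed). For a one-sample t interval, coverage of the drug effect is

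P(-t ≤ T ≤ t), where t = t(0.975, n-1) and T is noncentral t with n-1 df and noncentrality b√n.

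- n = 12: t = 2.201. For b = 0.5 the noncentrality is 0.5 × √12 = 1.732.
- n = 16: t = 2.131. For b = 0.5 the noncentrality is 0.5 × √16 = 2.0.

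| b (SD) | Coverage, n=12 | Coverage, n=16 |
|---|---|---|
| 0 | 95% | 95% |
| 0.1 | 93.8% | 93.4% |
| 0.25 | 87.6% | 84.5% |
| 0.5 | 64.7% | 53.5% |
| 1.0 | 11.7% | 3.8% |

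Simulation (100,000 runs per setting, at b = 0.25, 0.5 and 1.0) agrees to within 0.2 percentage points.

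**Step 3: active minus placebo at the same nominal time.** In the same simulations a two-sample t interval covered the drug effect in 94.9% to 95.1% of runs. Its cost is width, in SD units:

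- Within arm, t(n-1)/√n: 2.201/√12 = 0.64; 2.131/√16 = 0.53.
- Difference, t(2n-2) × √(2/n): 2.074 × √(2/12) = 0.85; 2.042 × √(2/16) = 0.72.

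**Step 4: a note on scale.** Step 3 takes the shift as additive on the percentage-change scale. If it is multiplicative, a drug effect d and a shift m give an active-arm change of (1+d)(1+m) - 1 and a placebo change of m. With d = 30% assumed, m = -10% gives 1.30 × 0.90 - 1 = 17%, and m = +20% gives 1.30 × 1.20 - 1 = 56%. Subtracting placebo leaves d(1+m), that is 0.30 × 0.90 = 27% and 0.30 × 1.20 = 36%. This is much closer to 30% but not exact. The ratio (1+d)(1+m)/(1+m) cancels m entirely.

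**The case against.** The case against is substantial. Randomized placebo subjects follow the same schedule, the active-placebo difference is already planned, and a shared shift cancels from it in expectation. A shift common to all arms also leaves the ordering of the doses unchanged and would show in the placebo column. The fasted predose samples at Visits 3 to 5 already give a like-for-like trough comparison. Section 3.2 frames the evaluation against placebo and sends the results to modeling and simulation; nothing visible says the dose will be picked from post-dose within-arm intervals. All of this stands and limits the importance of the point. It does not supply an interval for the placebo contrast or restrict the within-arm one.

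A reader might infer more than the documents support:

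- **That the protocol treats these markers as meal-sensitive.** It never says so. The overnight fast also applies to predose PK samples and to the hematology and chemistry draws, so it may be a convention for the whole visit.
- **That a plausible shift would make the placebo CI exclude zero.** This depends on the assumptions. With a true +20% shift and an SD of 30 points, both assumed, it happens in about 56% of trials at n=12 and 70% at n=16. At SD 40 the figures are 35% and 47%.
- **That all three markers are affected at Visits 6 and 7, or that a return-to-baseline reading is compromised there.** PPi is not collected at those visits, the fasting state at Visit 7 is contradictory, and no return-to-baseline analysis appears in the text.

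Table 3.2 and part of Section 11.5.2 are not visible, and Section 11.10 defers methods to a SAP whose detail is not in the available text. Meal instructions or a restriction of the CI could sit there. Standardizing meals would not by itself remove a fasted-to-fed difference.

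**Conclusion.** The point holds in a limited form. In the visible text the only 95% CI for the primary PD markers is on change from a normally fasted baseline, and it is not confined to times in the same state. That it is a within-arm interval is a reading of Section 11.5.3, which summarizes change by treatment group and treats the placebo difference separately. At the nonfasted times it cannot separate drug effect from meal or clock time. The contrast that can do so has no interval.

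The size is conditional. A shared shift of 0.25 SD would lower within-arm coverage of the drug effect to about 85-88%, and 0.5 SD to about 54-65%. With no shift there is no loss. The documents give no basis for choosing among these values. The calculation also assumes normally distributed percentage changes and a shift that is equal across arms and additive.

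The documents do not support a conclusion that the dose-response evaluation as a whole is biased. The trough comparisons at Visits 3 to 5 and the descriptive placebo differences are sound with respect to fasting state when the Day 1 predose sample is the baseline. This is a worthwhile wording change on a primary PD endpoint, not a design flaw.

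**What to change.** In Section 11.5.3 and the SAP, before database lock:

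1. Base the main dose-response CI for percentage change on the fasted predose samples at Visits 3, 4 and 5 against Day 1 predose.
2. Add a 95% CI for active minus placebo at each nominal time, state its scale (a ratio or log scale also removes a multiplicative shift), and use it to interpret the nonfasted times.
3. Keep the observed values and within-arm summaries at nonfasted times, labelled as nonfasted. They should not be dropped: Section 11.5.3 promises them, and Section 9.1 uses ALP, PLP and PPi for hypophosphatasia monitoring.
4. Reconcile the Visit 7 fasting rules (PD row against chemistry row) and the Visit 1 rules (PD row against Section 6.3). State how a screening value is handled when it serves as fallback baseline.
5. Align the synopsis, which gives the CI for PPi and PLP only, with Section 11.5.3, which adds ALP.

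The cost is wording, a few more table columns, and an amendment where the fasting rules change. No extra samples or visits are needed. The placebo-adjusted intervals are about a third wider than the within-arm ones (0.85/0.64 = 1.33 at n=12; 0.72/0.53 = 1.36 at n=16), and the within-arm post-dose CIs would no longer be the headline result.
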